## 6. Analysis Sets

### 6.1 Full Analysis Set

The full analysis set (FAS) includes all randomized subjects who received at least 1 dose of IP **excluding the 17 subjects that require additional Human Genetic Resource Administration office of China approval (Refer Section 3.2 for details)**. In efficacy analysis, subjects will be analyzed according to their randomized treatment group assignment.

### 6.2 Safety Analysis Set

Safety Analysis Set is same as the Full Analysis Set. For safety analyses, subjects will be grouped according to their actual treatment group (as defined in [Section 5.3](#)).

### 6.3 Study-specific Analysis Sets

#### Completers Analysis Set

The completer analysis set (CAS) includes subjects in the FAS who adhered to the scheduled IP regimen in the double-blind treatment period and have observed value for the co-primary endpoints.

## 7. Planned Analyses

### 7.1 Interim Analysis and Early Stopping Guidelines

No interim analysis is planned for this study.

### 7.2 Primary Analysis

The primary analysis will be performed, when all subjects have either completed the study, or have early terminated from the study. At that time, the database will be cleaned, processed, locked **and a snapshot will be taken**; the study will also be unblinded **for analyses. Based on the snapshot, efficacy and safety analyses will be performed**.

### 7.3 Final Analysis

Not applicable for this study.

## 8. Data Screening and Acceptance

### 8.1 General Principles

The objective of the data screening is to assess the quantity, quality, and statistical characteristics of the data relative to the requirements of the planned analyses.

### 8.2 Data Handling and Electronic Transfer of Data

The Amgen Global Study Operations-Data Management (GSO-DM) department will provide all data to be used in the planned analyses **including data from RAVE**

database and central lab data (outside of RAVE database). The database will be subjected to edit checks outlined in the Data Management Plan (DMP). Additional details will be provided in DMP and Data Acquisition Requirements Specifications (DARS).

### 8.3 Handling of Missing and Incomplete Data

#### 8.3.1 Patterns of Missing Data

Subjects may be missing specific data points for various reasons. In general, data may be missing due to a subject's early withdrawal from study, a missed visit, or non-evaluability of a data point or an endpoint at a particular point in time. All attempts will be made to capture missing or partial data for this trial prior to the database lock.

#### 8.3.2 Missing Lipid Measurements

For efficacy endpoints, where the analysis method is repeated measures linear effects model, missing lipid measurements will not be imputed. The handling of missing LDL-C response (50% reduction of LDL-C from baseline) and achievement of target LDL-C < 70 mg/dL is provided in [Section 5.3](#). Sensitivity analysis will be performed on the co-primary endpoints to evaluate the robustness of the missing at random assumption, used in the repeated measures linear effects model as described in [Section 9.5.1.1](#).

#### 8.3.3 Handling of Incomplete Dates

Adverse events and concomitant medications with completely or partially missing start dates will be queried. If after the query is resolved, the date is still incomplete with year only or year and month only, the start date will be imputed as described as below.

**Table 8-1. Imputation Rule for Incomplete Dates**

	Missing	Imputation	Exception
Start date (AE and concomitant medication)	Day	1	Default to Study Day 1 if an event starts the same year and month as Study Day 1
	Day/Month	1-Jan	Default to Study Day 1 if an event starts the same year as Study Day 1

#### **8.4 Detection of Bias**

This study has been designed to minimize potential bias by the use of randomization of subjects into treatment groups and the use of blinding. Other factors that may bias the results of the study include:

- Major protocol deviations likely to impact the analysis and interpretation of the efficacy endpoints.
- Subject level unblinding before final database lock and formal unblinding.

Important protocol deviations likely to impact the analysis and interpretation of the efficacy endpoints will be tabulated in the Clinical Study Report (CSR).

Any unblinding of individual subjects prior to formal unblinding of the study will be documented in the CSR. The impact of such unblinding on the results observed will be assessed. Data from subjects whose treatment assignments are unblinded prior to formal unblinding will be listed. The timing and reason for unblinding will be included in these listings.

Additional sensitivity and/or supplementary analyses may be included to assess the impact of potential biases on the co-primary endpoints. If any sensitivity analyses are required to evaluate potential biases in the study's conclusions, then the sources of the potential biases and results of the sensitivity and/or supplementary analyses will be documented in the CSR.

#### **8.5 Outliers**

Various methods, including univariate summaries, histograms, scatter plots, box plots, and line graphs, may be used to identify outliers in key safety and efficacy variables. Extreme data points will be identified during the blinded review of the data prior to database lock. Such data points will be reviewed with clinical data management to ensure accuracy. The primary analyses will include outliers in the data. Sensitivity analyses may be undertaken if extreme outliers for a variable are observed.

#### **8.6 Distributional Characteristics**

Distributional assumptions for the primary and secondary co-endpoints will be assessed. If the assumptions are not met, then alternative methods will be utilized. The use of alternative methods will be fully justified in the CSR.

#### **8.7 Validation of Statistical Analyses**

Programs will be developed and maintained and, output will be verified in accordance with current risk-based quality control procedures.

Tables, figures, and listings will be produced with validated standard macro programs where standard macros can produce the specified outputs.

The production environment for statistical analyses consists of Amgen-supported versions of statistical analysis software; for example, the SAS System version 9.4 or later.

## 9. Statistical Methods of Analysis

### 9.1 General Considerations

The efficacy and safety analyses will be performed on the FAS. Unless specified otherwise, the FAS will be the default analysis set in this study and data will be summarized by randomized treatment group **using the analysis window specified in Table 12-1**. Analyses will be performed separately by each dose frequency (Q2W and QM) unless specified otherwise.

[figure not shown]
Subject disposition, demographics, baseline characteristics and exposure to IP will be summarized by treatment group. Summary statistics for continuous variables will include the number of subjects, mean, median, SD or standard error, minimum, and maximum. For categorical variables, the frequency and percentage will be given.

Methods of handling missing data for efficacy endpoints will be described below. Missing data will not be imputed for safety endpoints.

#### Multiplicity Adjustment Method

The analyses of Q2W and QM will be performed as 2 independent experiments. To preserve the familywise error rate at 0.05 within each independent experiment (Q2W and QM), methods of adjusting for multiplicity due to multiple estimands (co-primary and secondary efficacy estimands) within each dose frequency are described in the diagram below ([Figure 9-1](#)).

Figure 9-1. Multiplicity Adjustment Methods

Testing of each estimand pair will result in a single p-value, and for co-secondary estimands these p-values will then be used in the Hochberg procedure. The following method will be used to preserve the family wise error rate for the co-primary and secondary estimands for testing within each dose frequency:

1. If the treatment effect from the primary analysis of the co-primary estimands are both significant at a significance level of 0.05, statistical testing of the tier 1 secondary efficacy estimands will follow the Hochberg procedure at a significance level of 0.005 ([Hochberg, 1988](#))
2. If all tier 1 secondary efficacy estimands are significant, the tier 2 secondary efficacy estimands will be tested using the Hochberg procedure at a significance level of 0.05.
3. If not all tier 1 secondary efficacy estimands are significant, the tier 2 secondary efficacy estimands will be tested using the Hochberg procedure at a significance level of 0.045 ([Wiens, 2003](#)).

Unless specified otherwise, all other hypothesis testing will be 2-sided with a significance level of 0.05.

## 9.2 Subject Accountability

The number of subjects who were screened, randomized, received IP, completed IP, discontinued IP and reasons for discontinuing, completed study, discontinued study and reasons for discontinuing, **including due to COVID-19, if applicable**, will be summarized by treatment group.

Key study dates for the first subject enrolled, last subject enrolled, last subject's end of IP and last subject's end of study will be presented.

**The number and percentage of subjects randomized will be tabulated by study site.**

The number and percent of subjects randomized will be tabulated by the stratification factors.

The number of subjects included in, and excluded from, each analysis set, and reason for exclusion will also be summarized.

## 9.3 Important Protocol Deviations

Important Protocol Deviations (IPDs) categories are defined by the study team before the first subject's initial visit and updated during the IPD reviews throughout the study prior to database lock. These definitions of IPD categories, subcategory codes, and descriptions will be used during the course of the study. Eligibility deviations are defined in the protocol.

**The number of subjects meeting Protocol Deviations due to COVID-19 will be summarized. A Protocol Deviations listing of subjects impacted due to COVID-19 will also be provided.**

## 9.4 Demographic and Baseline Characteristics

Demographic (ie, age, geriatric age group [ $< 65$ ,  $\geq 65$  and  $\geq 75$ ], sex, race, ethnicity) and baseline disease characteristics (cardiovascular medical history and lipid-regulating medication) will be summarized by treatment group and overall using descriptive statistics. If multiple races have been reported for a subject, the subject will be categorized as multiple race.

## 9.5 Efficacy Analyses

**Table 9-1. Primary Efficacy Endpoint Summary Table**

Endpoint	Primary Summary and Analysis Method (Specify Analysis Set if FAS is Not Used)	Sensitivity and/or Supplementary Analysis

Mean percent change from baseline at weeks 10 and 12 in LDL-C

Percent change from baseline at week 12 in LDL-C

	Repeated Measures Model assuming Missing at Random (MAR), including all values observed (on and off IP)	
Sensitivity analysis:
 

Multiple imputation to handle missing primary variables

Applying a separated analytical window to subjects who have protocol deviation code 953 (COVID-19 out-of-window visit).

 
Supplementary analysis:
 

Primary analysis will be repeated using CAS

Non-parametric analyses will be performed if assumption of normality is violated

**Table 9-2. Secondary Efficacy Endpoint Summary Table**

Endpoint	Primary Summary and Analysis Method (Specify Analysis Set if FAS is Not Used)	Sensitivity Analysis

Mean LDL-C achievement of target LDL-C < 70 mg/dL and LDL-C response of <math>\geq 50\%</math> reduction from baseline at weeks 10 and 12

LDL-C achievement and response at week 12

	Cochran Mantel-Haenszel (CMH) test	N/A
Mean percent change from baseline at weeks 10 and 12 Percent change from baseline at week 12 in each of the following lipid parameters: Lp(a), triglycerides, HDL-C and VLDL-C	Repeated measures model assuming MAR including all observed values (on and off IP)	N/A

### 9.5.1 Analyses of Primary Efficacy Endpoint(s)

To assess the co-primary endpoints as described in the co-primary estimands a repeated measures linear effects model including all observed values (on and off treatment) will be used on the FAS in each dose frequency to compare the efficacy of evolocumab with placebo. The repeated measures model will include terms for treatment group, stratification factor, scheduled visit and the interaction of treatment with scheduled visit. Missing values will not be imputed for primary analysis.

To account for the repeated LDL-C measurements within a subject across the visits, the repeated measures linear effects model will use an unstructured covariance.

Multiplicity adjustment procedures are defined in [Section 9.1](#).

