10.1.3 Covariates and Sub-groups

Baseline covariates and sub-groups include, but are not limited to:

- Stratification factors:
 - entry CV risk (high/very high CV risk vs not high/very high CV risk).
- Age: < 65 year, ≥ 65 years
- Sex

- Medical history of Diabetes (yes/no)
- Study baseline LDL-C: < median / \geq median
- Family history of premature coronary heart disease (yes/no)
- Baseline PCSK9
- Diagnosis of HeFH according to protocol defined criteria

Missing data will not be imputed for safety endpoints.

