#### 4. Covariates and Subgroups

##### 4.1 Planned Covariates

- **Stratification factor** - Entry CV risk (high/very high CV risk vs. not high/very high CV risk).

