###### Subgroup by baseline characteristics

- Age (< 65 years,  $\geq$  65 years)
- Sex (female, male)
- Medical history of Diabetes Mellitus (yes/no)
- Baseline LDL-C (< median,  $\geq$  median)
- Family history of premature CHD (yes, no)
- Baseline PCSK9: (< median,  $\geq$  median)
- Body Mass Index (BMI; < 25 kg/m^2, 25 - < 30 kg/m^2,  $\geq$  30 kg/m^2)
- Hypertension (yes, no)
- Current smoker (yes, no)
- Baseline CHD risk factors  $\geq$  2 (yes, no)
- Baseline triglycerides (< median,  $\geq$  median)
- Diagnosis of HeFH according to protocol defined criteria (yes/no)

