#### Baseline lipid and lipid related parameters

Baseline values for lipids (total cholesterol, HDL-C, **non-HDL-C**, LDL-C, VLDL-C and triglycerides), ApoA1, ApoB, Lp(a) and their derived parameters (eg, ratio between them) are defined as the mean of the two most recent non-missing concentrations measured through central lab prior to or on Study Day 1. If for any reason only 1 value is available, then that value will be used as baseline.

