#### 9.5.1.2 Covariate and Subgroup Analyses of Co-primary Endpoints

In addition to the primary analysis, covariate-adjusted analyses of the co-primary efficacy estimands will be performed as supportive analyses using the baseline covariates in [Section 4.2](#), one at a time, in the primary model used in the primary analyses as appropriate.

Subgroup analyses on the co-primary efficacy estimands will be conducted using the subgroups specified in [Section 4.2](#). Treatment effect differences among subgroups, which represent subgroup by treatment interactions, will be estimated and tested based on statistics from the subgroup repeated measures models.

For covariate and subgroup analyses, the stratification factor from the eCRF will be used. Differences in stratum assignment between data collection via IVRS and eCRF will be tabulated.

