### **9.5.2 Analyses of Secondary Efficacy Endpoint(s)**

The statistical model and testing of the tier 1 secondary efficacy endpoints as described in estimands supporting the secondary objectives, will be similar to the primary analysis of the co-primary estimands. The secondary estimands of achievement of target LDL-C < 70 mg/dL and LDL-C response of ≥ 50% reduction from baseline will be analyzed using the Cochran-Mantel Haenszel (CMH) test adjusted by the stratification factor.

Analyses of the tier 2 secondary efficacy estimands will use the same analysis model as the tier 1 estimands, Refer to [Section 9.1](#) and [Figure 9-1](#) for multiplicity adjustment for multiple tier 1 and tier 2 secondary endpoints.

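### The confirmatory repeated-measures model leaves out the baseline value of the analysed lipid; adding it is a small, cheap gain in precision, largest for absolute LDL-C change

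*SAP*

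**What the plan says.** SAP 9.5.1 states: "The repeated measures model will include terms for treatment group, stratification factor, scheduled visit and the interaction of treatment with scheduled visit". It uses an unstructured covariance and no imputation. Protocol 10.5.2.1 lists the same four terms. SAP 4.1 names one planned covariate, the two-level entry CV-risk stratum. Under SAP 9.5.2 the tier 1 continuous endpoints get a similar model, and the tier 2 endpoints "will use the same analysis model as the tier 1 estimands".

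The baseline lipid is available in good quality. SAP 5.2 defines it as the "mean of the two most recent non-missing concentrations measured through central lab prior to or on Study Day 1", and protocol Table 2 schedules the lipid panel, ApoB and Lp(a) at both screening and Day 1.

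Some baseline adjustment is planned. SAP 9.5.1.2 says "covariate-adjusted analyses of the co-primary efficacy estimands will be performed as supportive analyses using the baseline covariates" in SAP 4.2, one at a time. That list shows baseline LDL-C split at the median. So does protocol 10.1.3, whose list opens with "Baseline covariates and sub-groups include, but are not limited to" and contains "Study baseline LDL-C: < median" and its complement. No counterpart is planned for the tier 1 or tier 2 continuous endpoints.

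**The concern.** The pre-treatment value of the lipid itself is an obvious prognostic covariate, yet every confirmatory continuous analysis omits it. Two things follow.

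First, intervals are somewhat wider than they need be. Second, subtracting or dividing by baseline does not fully remove a chance baseline imbalance. Whatever slope of change (or percent change) on baseline remains stays in the treatment estimate, and only about 67 placebo subjects are expected to be analysed per dose frequency.

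The loss should be greatest for absolute LDL-C change. A roughly proportional drug effect makes that change depend directly on baseline in the active arm.

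**Working it through.** **1. The plan's own power.** Inputs from SAP 3.2: effect 40, SD 25, 150 versus 75 per dose frequency, 10% dropout, 0.05 for each co-primary (taken as two-sided). Analysed: 135 versus 67.

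SE = 25 × √(1/135 + 1/67) = 3.74; 40/3.74 = 10.7.

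Power per endpoint exceeds 99.99%. The plan's products (0.99 × 0.99 = 0.980; 0.98 × 0.98 = 0.960) reproduce as conservative lower bounds. Removing 18 subjects in proportion leaves (450 − 18) × 75/450 × 0.9 ≈ 65 placebo per regimen, still above 99.99%.

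**2. Percent change, simple formula.** If baseline and outcome correlate ρ within stratum in both arms, variance is multiplied by 1 − ρ². With 135 versus 67.5, SE is 3.73 and the 95% half-width 7.30 without baseline.

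- ρ = 0.1: SE 3.71, half-width 7.27, variance −1%
- ρ = 0.2: SE 3.65, half-width 7.16, variance −4%
- ρ = 0.3: SE 3.56, half-width 6.97, variance −9%

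**3. Absolute change, analytic.** Let b1 and b0 be the active and placebo slopes of change on baseline, s the within-stratum baseline SD and t the residual SD.

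- Without baseline: V = (b1²s² + t²)/135 + (b0²s² + t²)/67.5.
- With baseline: replace each slope by its distance from b*. For a common slope, b* = (2·b1 + b0)/3. For arm-specific slopes with baseline centred at the overall mean, b* = (b1 + 2·b0)/3.

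Example with assumed b1 = −0.6, b0 = −0.15, s = t = 20:

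- No baseline: 544/135 + 409/67.5 = 10.09
- Common slope (b* = −0.45): 409/135 + 436/67.5 = 9.49, a fall of 5.9%
- Arm-specific (b* = −0.30): 436/135 + 409/67.5 = 9.29, a fall of 7.9%

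Over s of 20 to 30, active residual SD 20 to 25 (placebo 20) and b1 of −0.4 to −0.6, the common-slope gain is 0% if b0 = 0, 4–12% if b0 = −0.15 and 9–24% if b0 = −0.30. Arm-specific slopes give 1–7%, 4–16% and 9–26%. With 2:1 allocation a pooled-variance common-slope model would report falls of about 5–35% over the same grid, more than is truly gained.

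**4. Simulation.** 135 versus 67, complete data, 12,000 replicates per setting. Per-visit or two-visit-mean regression on treatment and stratum, with and without the raw two-sample baseline.

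Assumed for LDL-C: log SD 0.3, mean 110 mg/dL, the protocol's entry thresholds (80 mg/dL for the high-risk stratum, 130 otherwise), 18% or 6% not high risk, 60% proportional reduction. Response log SD is 0.35 (percent-change SD 13–22%) or, as the wider spread, 0.6 (21–27%). Assumed for other lipids: no thresholds, 7% effect.

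Percent fall in variance of the treatment difference, by visit-to-visit correlation:

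| Endpoint | 0.6 | 0.7 | 0.8 | 0.9 |
|---|---|---|---|---|
| LDL-C % change, week 12 (18% not high risk) | 3.2 | 1.9 | 1.0 | −0.3 |
| same, 6% not high risk | 3.7 | 1.5 | 1.1 | 0.0 |
| same, wider spread | 1.4 | 1.1 | 0.1 | −0.5 |
| LDL-C % change, mean of weeks 10 and 12 | 4.9 | 2.5 | 1.3 | −0.2 |
| Absolute LDL-C, with baseline-by-treatment | 15.0 | 13.5 | 12.8 | 12.1 |
| same, 6% not high risk | 16.0 | 13.5 | 14.1 | 14.0 |
| same, wider spread | 8.9 | 8.2 | 6.6 | 5.2 |
| Absolute LDL-C, common slope | 13.4 | 10.4 | 9.0 | 3.8 |
| Other lipids, log SD 0.25, week 12 | 7.4 | 5.0 | 3.1 | 1.5 |
| same, mean of weeks 10 and 12 | 11.4 | 7.9 | 4.8 | 2.2 |
| Other lipids, log SD 0.45, week 12 | 6.7 | 4.5 | 2.6 | 1.4 |

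For the other lipids a median split recovered about 55–70% of the continuous-baseline gain (2/π = 64% under normality).

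**5. In practical terms.** A 1-SE baseline imbalance moves LDL-C percent change by 0.5 to 0.1 points and other lipids by 1.4 to 0.2 points. A 4% variance gain narrows an interval by 1 − √0.96 = 2% and equals 0.04 × 225 = 9 subjects. It would lift a single 80%-powered test to Φ(2.80/√0.96 − 1.96) = 81.6%. The power figure is illustrative only, since the documents state no tier 2 effect or power.

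**The case against.** The strongest reply is that nothing is wrong: a randomised comparison adjusted for the stratification factor is valid, prespecified and the same in both documents. That stands, and it is why the point is optional.

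Baseline is also partly handled already. Percent change divides by it, the two-sample mean limits regression to the mean, and the stratum carries baseline LDL-C through the entry thresholds. The simulation has the stratum and thresholds in both models, so its gains are net of them. The supportive analysis in SAP 9.5.1.2 helps the co-primaries. The SAP does not say in what form its covariates enter, so a continuous term is not ruled out there. It does nothing for the secondary endpoints.

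The gain is largest where power is least needed. For an assumed difference of 32 mg/dL (40% of the 80 mg/dL floor) and SD up to 40, power for absolute change already exceeds 99% at 0.005. That stands too.

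The sizes depend on assumptions. With a 40% effect and active-arm SD near 25%, another run gave about 12% to 8% for absolute change with the interaction; two further settings near that SD gave about 12% to 4%. For very skewed lipids (log SD 0.9–1.1) the week 12 gain was about 3% to 1%. The ranking survives, but the upper figures are not guaranteed.

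Finally, SAP version 2.0 is dated 30 November 2020 and already describes subjects as enrolled. Changing a confirmatory model that late needs care over timing and documentation.

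**Conclusion.** The point holds as an optional improvement in efficiency. The confirmatory model omits a baseline value that is already measured twice, and the tier 1 and tier 2 continuous endpoints have no planned baseline adjustment.

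The benefit is small to nil for LDL-C percent change, modest for the other lipids, and largest for absolute LDL-C change. These sizes rest on assumed correlations, spreads and effects, because the documents supply no baseline SD, baseline-outcome correlation or mg/dL SD. The common-slope gain for absolute change vanishes if the placebo slope is exactly zero. Regression to the mean makes that unlikely, and the centred interaction protects against it. Confidence in the omission is high, and in the exact size moderate.

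**What to change.** Before unblinding:

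- Add the continuous baseline value of the analysed parameter, and its interaction with visit, to the repeated-measures model for the co-primary, tier 1 and tier 2 continuous endpoints. List it in SAP 4.1.
- For absolute LDL-C change, also add baseline-by-treatment, with baseline centred at the overall mean.
- Keep the unadjusted model as a supportive analysis.
- Record the departure from protocol 10.5.2.1 in SAP Section 10.

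The cost is wording in SAP 4.1, 9.5.1 and 9.5.2, two model terms (three for absolute LDL-C change), the supportive runs and one Section 10 entry. No new data are needed. The downside is a possible rise of up to about 0.5% in the LDL-C percent-change variance if the visit-to-visit correlation is as high as 0.9.
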